7.4 Dosage Modification

There is no provision for dose modification of study intervention. If a participant interrupts intervention due to an AE, study intervention can be restarted in consultation with the Sponsor Medical Monitor or designee.

7.5 Preparation/Handling/Storage/Accountability

The IP/Non-IMP/AxMP must be stored in a secure area according to local regulations. It is the responsibility of the investigator, or designee where permitted, to ensure that IP/IMP/Non-IMP/AxMP is only dispensed to study participants. The IP/IMP/Non-IMP/AxMP must be dispensed only from official study sites by authorized personnel according to local regulations.

The product storage manager should ensure that the study intervention is stored in accordance with the environmental conditions (temperature, light, and humidity) as determined by the Sponsor. If concerns regarding the quality or appearance of the study intervention arise, the study intervention should not be dispensed, and the Sponsor should be contacted immediately.

Study intervention not supplied by the Sponsor will be stored in accordance with the package insert.

IP/IMP/Non-IMP/AxMP documentation (whether supplied by the Sponsor or not) must be maintained and must include all processes required to ensure the drug is accurately administered. This includes documentation of drug storage, administration and, as applicable, storage temperatures, reconstitution, and use of required processes (eg, required diluents, administration sets).

- The investigator or designee must confirm that appropriate temperature conditions have been maintained during transit for all study intervention received and any discrepancies are reported and resolved before use of the study intervention.
- Only participants enrolled in the study may receive study intervention, and only authorized site staff may supply, prepare, or administer study intervention.
- All study intervention must be stored in a secure, environmentally controlled, and monitored (manual or automated) area in accordance with the labeled storage conditions with access limited to the investigator and authorized site staff.
- The investigator, institution, head of the medical institution (where applicable), or authorized site staff is responsible for study intervention accountability, reconciliation, and record maintenance (ie, receipt, reconciliation, and final disposition of records).
- Further guidance and information for the final disposition of unused study interventions are provided in the Pharmacy Manual.

7.6 Study Intervention Compliance

When participants self-administer study intervention(s) at home, compliance with study intervention will be assessed at each visit. Compliance will be assessed by direct questioning, counting returned tablets, etc during the site visits and documented in the source documents and relevant form. Deviation(s) from the prescribed dosage regimen should be recorded in the Case Report Form (CRF).

A record of the quantity of BMS-986322/placebo dispensed to and administered by each participant must be maintained and reconciled with study intervention and compliance records.

Intervention start and stop dates, including dates for intervention delays and/or dose reductions, will also be recorded in the CRF.

7.7 Concomitant Therapy

7.7.1 Prohibited and/or Restricted Treatments

Prohibited and/or restricted medications taken prior to study intervention administration in the study are described below in Table 7.7.1-1. Medications taken within 4 weeks prior to study intervention administration must be recorded on the CRF.

Table 7.7.1-1: Prohibited and/or Restricted Treatments

Tuble / / / I	110mbited and/of Restricted 11eacments	
Prohibited Treatments		Washout Period (Before Randomization)
Lithium, antimalarials		4 weeks
Metformin or statins		Restrict dose of metformin to 500 mg twice a day or 850 mg once a day with plasma lactate monitoring or switch to other glucose-lowering agents;

Table 7.7.1-1: Prohibited and/or Restricted Treatments

Prohibited Treatments	Washout Period
	(Before Randomization)
	atorvastatin ($\leq 20 \text{ mg}$) rosuvastatin ($\leq 10 \text{ mg}$) simvastatin ($\leq 20 \text{ mg}$) Pravastatin ($\leq 20 \text{ mg}$) lovastatin ($\leq 20 \text{ mg}$) Fluvastatin ($\leq 40 \text{ mg}$) pitavastatin ($\leq 2 \text{ mg}$)

Therefore, drugs that are sensitive substrates of these transporters are recommended to be used with caution or their dose restricted for the duration of the study. Additional references^{54,55} and individual drug labels should be referred to for further information on PK drug-drug interactions.

In addition, the use of concomitant medications (prescription, over-the-counter) should be limited during the study unless they are prescribed by the investigator for treatment of specific clinical events and after consultation with the Sponsor Medical Monitor. Any changes to or new concomitant therapies must be recorded on the CRF.

The use of herbal products is prohibited during and up to 30 days after the completion of the study.

7.7.2 Other Restrictions and Precautions

See Section 6.3 for details regarding sun exposure restrictions.

7.8 Continued Access to Study Intervention After the End of the Study

At the end of the study, the Sponsor will not continue to provide Sponsor-supplied study intervention to participants/investigators unless the Sponsor chooses to extend the study. The investigator should ensure that the participant receives appropriate standard of care to treat the condition under study.

The Sponsor reserves the right to terminate access to Sponsor-supplied study intervention if any of the following occur: a) the study is terminated due to safety concerns; b) the development of BMS-986322 is terminated for other reasons, including, but not limited to, lack of efficacy and/or not meeting the study objectives; or c) the participant can obtain medication from a government-sponsored or other health program. In all cases, the Sponsor will follow local regulations.

8 DISCONTINUATION CRITERIA

Discontinuation of specific sites or of the study as a whole is detailed in Appendix 2.

8.1 Discontinuation of Study Intervention

Participants MUST discontinue IP/IMP (and Non-IMP/AxMP at the discretion of the investigator) for any of the following reasons:

- Participant's request to stop study intervention. Participants who request to discontinue study intervention will remain in the study and must continue to be followed for protocol-specified follow-up procedures. The only exception to this is when a participant specifically withdraws consent for any further contact with him/her or persons previously authorized by the participant to provide this information.
- Any clinical AE, laboratory test result abnormality, or intercurrent illness which, in the opinion of the investigator, indicates that continued participation in the study is not in the best interest of the participant.
- Termination of the study by the Sponsor.
- Loss of ability to freely provide consent through imprisonment or involuntary incarceration for treatment of either a psychiatric or physical illness (eg, infectious disease). (Note: Under specific circumstances and only in countries where local regulations permit, a participant who has been imprisoned may be permitted to continue as a participant. Strict conditions apply, and Sponsor approval is required.)
- Significant noncompliance with protocol (eg, procedures, assessments, medications, etc). The investigator should discuss such issues with the Sponsor Medical Monitor.
- Any current evidence of SARS-CoV-2 infection.
- If a participant is unblinded for any reason.
- Permanent discontinuation of the study intervention for abnormal liver tests should be considered by the Investigator when a participant meets one of the conditions outlined in Section 9.2.7 or if the Investigator believes that it is in best interest of the participant.
- Pregnancy (see Section 9.2.5).

Refer to the Section 2: Schedule of Activities for data to be collected at the time of treatment discontinuation and follow-up and for any further evaluations that can be completed.

All participants who discontinue study intervention should comply with protocol-specified follow-up procedures as outlined in Section 2: Schedule of Activities. The only exception to this requirement is when a participant withdraws consent for all study procedures, including post-treatment study follow-up, or loses the ability to consent freely (eg, is imprisoned or involuntarily incarcerated for the treatment of either a psychiatric or physical illness).

If study intervention is discontinued prior to the participant's completion of the study, the reason for the discontinuation must be documented in the participant's medical records per local regulatory requirements in each region/country and entered on the appropriate CRF page.

8.1.1 Post-study Intervention Study Follow-up

Participants who discontinue study intervention may continue to be followed.

8.2 Discontinuation From the Study

Participants who request to discontinue study intervention will remain in the study and must continue to be followed for protocol-specified follow-up procedures. The only exception to this is when a participant specifically withdraws consent for any further contact with him/her or persons previously authorized by the participant to provide this information.

- Participants should notify the investigator of the decision to withdraw consent from future follow-up.
- The withdrawal of consent should be explained in detail in the medical records by the investigator as to whether the withdrawal is from further treatment with study intervention only or also from study procedures and/or post-treatment study follow-up, and entered on the appropriate CRF page.
- In the event that vital status (whether the participant is alive or dead) is being measured, publicly available information should be used to determine vital status only as appropriately directed in accordance with local law.
- If the participant withdraws consent for disclosure of future information, the Sponsor may retain and continue to use any data collected before such a withdrawal of consent.

8.2.1 Individual Discontinuation Criteria

- A participant may withdraw completely from the study at any time at his/her own request, or may be withdrawn at any time at the discretion of the investigator for safety, behavioral, compliance, or administrative reasons. This is expected to be uncommon. Stopping study intervention is not considered withdrawal from the study.
- At the time of discontinuing from the study, if possible, an ET visit should be conducted, as shown in the Schedule of Activities. See the Schedule of Activities (Section 2) for data to be collected at the time of study discontinuation and follow-up and for any further evaluations that need to be completed.
- The participant will be permanently discontinued from both the study intervention and the study at that time. No follow-up visit will be performed where a participant withdraws consent.
- If the participant withdraws consent for disclosure of future information, the Sponsor may retain and continue to use any data collected before such a withdrawal of consent.

8.2.2 Study Termination for Unexpectedly Unfavorable Risk/Benefit Balance

The DMC will evaluate the risk/benefit profile of the study on an ongoing basis. This evaluation will be based on all available unblinded data with particular attention to: (1) AEs or other safety trends in this or any other clinical study of BMS-986322 whose character, severity, and/or frequency suggest that participants would be exposed to an unreasonable and significant risk of illness or injury; (2) new nonclinical data suggesting unreasonable and significant risk of illness or injury. In addition, the Sponsor will evaluate the blinded data on an ongoing basis for unexpected/unusual safety findings/signals and increases in PsO disease activity and/or discontinuations not anticipated in a clinical trial of similar participant populations. Any concerns

will be escalated promptly to the DMC for further evaluation.

If such evaluation suggests that the risk/benefit profile of the study or an individual dose group has become unfavorable to the study participants, the Sponsor will pause enrollment and/or dosing until further assessment of data and interaction with the appropriate Health Auhtority(ies) can take place on potential actions. Such actions may include, but are not limited to, study continuation without change, continuation with modification, or termination of the study.

8.3 Lost to Follow-up

The following actions must be taken if a participant fails to return to the clinic for a required study visit:

- All reasonable efforts must be made to locate participants to determine and report their ongoing status. This includes follow-up with persons authorized by the participant.
- Lost to follow-up is defined by the inability to reach the participant after a minimum of 3 documented phone calls, faxes, or emails, as well as lack of response by participant to 1 registered mail letter. All attempts should be documented in the participant's medical records.
- If the investigator's use of a third-party representative to assist in the follow-up portion of the study has been included in the participant's informed consent, then the investigator may use a Sponsor-retained third-party representative to assist site staff with obtaining the participant's contact information or other public vital status data, such as public health registries and databases, necessary to complete the follow-up portion of the study.
- The site staff and representative will consult publicly available sources, such as public health registries and databases, to obtain updated contact information.
- If, after all attempts, the participant remains lost to follow-up, then the last known alive date as determined by the investigator should be reported and documented in the participant's medical records.
- If it is determined that the participant has died, the site will use permissible local methods to obtain date and cause of death.

9 STUDY ASSESSMENTS AND PROCEDURES

- Study procedures and timing are summarized in the Schedule of Activities, see Section 2.
- Protocol waivers or exemptions are not allowed.
- All immediate safety concerns must be discussed with the Sponsor immediately upon occurrence or awareness to determine whether the participant should continue or discontinue treatment.
- Adherence to the study design requirements, including those specified in the Schedule of Activities (see Section 2), is essential and required for study conduct.
- All screening evaluations must be completed and reviewed to confirm that potential participants meet all eligibility criteria before randomization. The investigator will maintain a

screening log to record details of all participants screened and to confirm eligibility or record reasons for screening failure, as applicable.

[figure not shown]
- Procedures conducted as part of the participant's routine clinical management (eg, complete blood count) and obtained before signing of informed consent may be utilized for screening or baseline purposes provided the procedure meets the protocol-defined criteria and has been performed within the time frame defined in the Schedule of Activities, see Section 2.
- For several assessments, appropriate training will be provided to investigators and designated personnel at sites. Only those individuals trained and certified to perform these assessments will be performing them during the study.
- Repeat or unscheduled samples may be taken for safety reasons or for technical issues with the samples.
- As part of the online questionnaire, the study sponsor may collect and use information about the gender that participants identify with, sexual orientation, and intersex status. At the conclusion of the study, summaries of this information, including information already collected about race, ethnicity, and gender, across all study participants will be developed to understand the populations that participated in the study. In addition, in the future, this data may be combined with data from other BMS studies to conduct subsequent research on how the disease or treatment impacts certain populations. Answering the questions about the gender you identify with, sexual orientation, and intersex status is voluntary, and participants are not required to answer these questions in the questionnaire to take part in this clinical study.

9.1 Efficacy Assessments

9.1.1 Efficacy Assessment for the Study

Every effort must be made to ensure that the same evaluator(s) complete the assessment for each participant. If the evaluator(s) is/are unable to complete the evaluation, then a qualified individual with overlapping experience may perform the evaluation. Documentation of who performed the evaluation is to be recorded in source documents. Assessments are to be performed at approximately the same time of day throughout the duration of the study.

Baseline assessments must be performed per protocol (standard of care assessments may not be used for baseline). Procedures not specified in the protocol that are part of standard care may be performed if they do not interfere with study procedures; any data arising from such procedures are not to be reported in the electronic CRF (eCRF).

9.1.3 Psoriasis Area and Severity Index (PASI)

The PASI is a measure of the average redness, thickness, and scaliness of psoriatic skin lesions (each graded on a 0-4 scale), weighted by the area of involvement (head, arms, trunk to groin, and legs to top of buttocks). The PASI produces a numeric score that can range from 0 to 72, with higher PASI scores denoting more severe disease activity. PASI can also be used to assess response to treatment. The PASI-50 is the proportion of participants who experience at least a 50% improvement in PASI score as compared with baseline value. The PASI-75, PASI-90, and PASI-100 are defined similarly. BMS will host a training session prior to initiation of the study to demonstrate proper PASI scoring. PASI assessments should be performed by a dermatologist or appropriately trained investigator who is experienced in the assessment of PsO patients (see Appendix 5 for an illustrative example).

Protocol Amendment No.: 01

Approved v2.0 930193109 2.0

9.2 Adverse Events

The definitions of an AE or SAE can be found in Appendix 3.

AEs will be reported by the participant (or, when appropriate, by a caregiver or a surrogate).

The investigator and any qualified designees are responsible for detecting, documenting, and reporting events that meet the definition of an AE or SAE and remain responsible for following up on AEs that are serious, considered related to the study intervention or the study, or that caused the participant to discontinue before completing the study.

Refer to Appendix 3 for SAE reporting.

9.2.1 Period and Frequency for Collecting AE and SAE Information

All AEs and SAEs must be collected from the time of signing the consent, including those thought to be associated with protocol-specified procedures and until 30 days following discontinuation of dosing.

The investigator must report any SAE that occurs after these periods and that is believed to be related to a study intervention or protocol-specified procedure (eg, a follow-up).

- All SAEs will be recorded and reported to the Sponsor or designee, promptly and not to exceed 24 hours of awareness of the event, as indicated in Appendix 3.
- The investigator will submit any updated SAE data to the Sponsor or designee within 24 hours of updated information being available.

Investigators are not obligated to actively seek AEs or SAEs in former study participants. However, if the investigator learns of any SAE, including a death, at any time after a participant has been discharged from the study, and he/she considers the event reasonably related to the study intervention or study participation, the investigator must promptly notify the Sponsor.

The method of evaluating and assessing causality of AEs and SAEs and the procedures for completing and reporting/transmitting SAE reports are provided in Appendix 3.

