The safety and tolerability of BMS-986322 will be assessed by the type, frequency, relationship, severity, and seriousness of treatment-emergent adverse events (AEs), clinical laboratory tests, 12-lead electrocardiogram (ECG), vital signs, and physical examination (PE). Treatment-emergent AEs and study intervention-related AEs and SAEs will be summarized using counts and percentages of participants experiencing the event as well as the number of events by system organ class, preferred term, and treatment group. PE findings, vital signs, clinical laboratory test results, and ECG test results will be summarized using descriptive summary statistics for continuous variables and frequency distributions (counts and percentages) for categorical variables. All safety analyses will be performed on the Safety Analysis Set.

Data Monitoring Committee: Yes

An Independent Data Monitoring Committee will be used in the study.

Other Committee: No

Other committees will not be used in this study.

Brief Summary:

The purpose of this study is to compare the proportion of moderate-to-severe PsO participants achieving PASI-75 score (≥ 75% reduction from baseline in PASI) between treatment and placebo groups at Week 12. Study details include the following:

Study Duration: 16 weeks

Study Intervention Duration: 12 weeks

Study Visit Frequency: Participants will report to the clinic for study visits on study Days , and, if applicable, Early Termination.

Protocol Amendment No.: 01

930193109 2.0

Approved v2.0

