Serology	X	Serum for hepatitis C antibody, HBsAg, anti-hepatitis B core antibody, anti-HBsAb, HIV-1 and -2 antibody (HIV viral RNA or p24 antigen, if needed) at screening only. See Section 9.4.8.
Urinalysis	X	Participants are required to fast for at least 8 hours prior to the collection of specimens for clinical laboratory tests. See Section 9.4.8.
Test for Drugs of Abuse	X	Urine or serum. See Section 9.4.8.
Tuberculosis Test (Interferon-gamma Release Assay)	X	In accordance with BMS standard testing at screening only. See Section 9.4.2.
Pregnancy Test (Serum)	X	Female participant only (see Appendix 4). Serum (minimum sensitivity equivalent units 25 IU/L or equivalent units of hCG) to be done at screening visit. The participant must be excluded from participation if the serum pregnancy result is positive.
FSH	X	If needed to document postmenopausal status, as defined in Appendix 4, at screening only. Females under the age of 55 years must have a serum FSH level > 40 mIU/mL to confirm menopause.
SARS-CoV-2 testing	X	PCR testing and other measures (eg, antibody testing, social distancing, temperature readings, personal protective equipment) that may be required by the site will be implemented.
Efficacy Assessments		

Protocol Amendment No.: 01

Clinical Protocol
BMS-986322
TYK2 inhibitor

Table 2-1: Screening Procedural Outline

Procedure	Screening	Notes
PASI	X	See Section 9.1.3 and Appendix 5 for an illustrative example.

AE Reporting		
Monitor for AEs and SAEs	X	All AEs and SAEs must be collected from the date of participant's written consent until 30 days following discontinuation of dosing or participant's participation in the study if the last scheduled visit occurs at a later time. See Section 9.2 and Appendix 3.

Abbreviations: AE, adverse event; BMI, body mass index; BMS, Bristol-Myers Squibb Company; ; ECG, electrocardiogram; FSH, follicle-stimulating hormone; HBsAb, hepatitis B surface antibody; HBsAg, hepatitis B surface antigen; hCG, human chorionic gonadotropin; HIV, human immunodeficiency virus; ; PASI, Psoriasis Area and Severity Index; PCR, polymerase chain reaction; PE, physical examination; PsA, psoriatic arthritis; ; RNA, ribonucleic acid; SAE, serious adverse event; SARS-CoV-2, severe acute respiratory syndrome coronavirus 2;

Protocol Amendment No.: 01

 Table 2-2:
 Follow-up Procedural Outline

							Follow-up Visit	Notes
Procedure ^a								
Safety Assessments								
Complete PE	X	X	X	X	X	X	X	See Section 9.4.1.
Weight	X			X	X	X	X	

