Vital Signs	Х	Х	X	X	Х	X	X	Includes (ear or oral) body temperature, respiratory rate, seated blood pressure, and heart rate. Blood pressure and heart rate should be measured after the participant has been resting quietly for at least 5 minutes.
12-lead ECG	X	X	X	X	X	Х	X	12-lead ECGs should be recorded after the participant has been supine for at least 5 minutes. A single ECG will be collected. See Section 9.4.3.
Concomitant Medication Use	Continuously						Concomitant medications should be reviewed and updated at each visit. See Section 7.7.	

 Table 2-2:
 Follow-up Procedural Outline

							Follow-up Visit	Notes
Procedure ^a								
Laboratory Tests								
Hematology	X^{b}	X	X	X	X	X	X	Including complete blood count with differential. Participants are required to fast for at least 8 hours prior to the collection of specimens for clinical laboratory tests on Day , and ET. See Section 9.4.8.
Chemistry	$X^{\mathbf{b}}$	X	X	X	X	X	X	Participants are required to fast for at least 8 hours prior to the collection of specimens for clinical laboratory tests on Day and ET. Fasting glucose and fasting C-peptide will only be taken on fasting days (Day and ET). See Section 9.4.8.
hsCRP	X ^b			X	X	X		Participants are required to fast for at least 8 hours prior to the collection of specimens for clinical laboratory tests on Day and ET. See Section 9.4.8.

 Table 2-2:
 Follow-up Procedural Outline

							Follow-up Visit	Notes
Procedure ^a								
Fasting Lipid Panel	X ^b					X		Participants are required to fast for at least 8 hours prior to the collection of specimens for clinical laboratory tests on Day and ET. See Section 9.4.8.
Urinalysis	X ^b	X	X	X	X	X	Х	Participants are required to fast for at least 8 hours prior to the collection of specimens for clinical laboratory tests on Day and ET. See Section 9.4.8.
Test for Drugs of Abuse	X ^b							Urine or serum. See Section 9.4.8.
Pregnancy Test (Urine)	Xb			X	X	X	X	All women must have a negative pregnancy test prior to dosing on Day .
AE Reporting								
Monitor for AEs and SAEs		Continuously						All AEs and SAEs must be collected from the date of participant's written consent until 30 days following discontinuation of dosing or participant's participation in the study if the last scheduled visit occurs at a later

							Follow-up Visit	Notes
Procedure ^a								
								time. See Section 9.2 and Appendix 3.
E CC"								
Efficacy Assessments								

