10.4.3 Primary Endpoint(s)

The primary objective of this study is to evaluate the response rate in PASI-75 after 12 weeks of treatment with BMS-986322. The response rate in PASI-75 is defined as the proportion of participants with moderate-to-severe PsO experiencing a 75% improvement (reduction from baseline) in PASI score at Week 12 (Day 85) and will be evaluated on the Full Analysis Set.

The safety and tolerability of BMS-986322 will be assessed by the type, frequency, relationship, severity, and seriousness of treatment-emergent AEs, clinical laboratory tests, 12-lead ECG, vital signs, and PE. Treatment-emergent AEs and study intervention-related AEs and SAEs will be summarized using counts and percentages of participants experiencing the event as well as the number of events by system organ class, preferred term, and treatment group. PE findings, vital signs, clinical laboratory test results, and ECG test results will be summarized using descriptive summary statistics for continuous variables and frequency distributions (counts and percentages) for categorical variables. All safety analyses will be performed on the Safety Analysis Set. An overview of primary efficacy and safety endpoints is given in Table 10.4.3-1.

Table 10.4.3-1: Primary Efficacy and Safety Endpoints

Primary Endpoint	Description	Time Frame
Achievement of PASI-75	At least 75% improvement in PASI score as compared to baseline, ie, percent change from baseline less than or equal to -75%	Week 12
Incidence of TEAEs	Type and frequency of TEAEs, SAEs, and TEAEs leading to treatment discontinuation Severity and causal relationship of TEAEs	30 days after last dose of study intervention or date of last follow-up, whichever is later
Clinical laboratory tests	Change from baseline and incidence of marked abnormalities	30 days after last dose of study intervention or date of last follow-up, whichever is later

Table 10.4.3-1: Primary Efficacy and Safety Endpoints

Primary Endpoint	Description	Time Frame	
12-lead ECG	Change from baseline and incidence of abnormal findings	30 days after last dose of study intervention or date of last follow-up, whichever is later	
Vital signs	Change from baseline and incidence of marked abnormalities	30 days after last dose of study intervention or date of last follow-up, whichever is later	

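### Section 9.2.1 ends AE and SAE collection 30 days after dosing stops, which is shorter than the schedule and the primary safety time frame for participants who stop treatment early and stay in the study

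*Combined protocol and SAP*

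**What the plan says.** Four places in the protocol set an end date for adverse event data, and one differs from the other three.

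- **Section 9.2.1** collects all AEs and SAEs from consent "until 30 days following discontinuation of dosing". After that it requires only SAEs believed related to the study intervention or a protocol procedure.
- **Table 2-1** (Section 2) collects them "until 30 days following discontinuation of dosing or participant's participation in the study if the last scheduled visit occurs at a later time". **Table 2-2** repeats the rule and marks the AE row as continuous. Both rows refer the reader to Section 9.2 and Appendix 3.
- **Table 10.4.3-1** (Section 10.4.3) gives the time frame for TEAEs and the other primary safety endpoints as "30 days after last dose of study intervention or date of last follow-up, whichever is later".

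On who is still being followed, Section 8.2 (and 8.1 in the same terms) says that participants who ask to stop study intervention "will remain in the study and must continue to be followed for protocol-specified follow-up procedures". Section 8.1 also says that everyone who discontinues study intervention should comply with the follow-up procedures in the schedule. Section 8.1.1 is weaker and says only that they may continue to be followed. Under Section 8.2.1, withdrawal from the study ends treatment and participation together.

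On timing, the Brief Summary gives "Study Duration: 16 weeks" and 12 weeks of treatment. The visit days are redacted.

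**The concern.** TEAE type, frequency, severity and relationship are primary endpoints. Their collection rule in Section 9.2.1 is shorter than their analysis window in Table 10.4.3-1. Completers hardly notice, because 30 days after the last dose falls at about the end of the study. A participant who stops early but keeps attending visits has a stretch of follow-up that the analysis table counts and Section 9.2.1 does not collect.

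Two things are at stake. First, ascertainment could depend on which section a site treats as the rule. Second, TEAEs are summarised as counts and percentages of participants, and the protocol text describes no adjustment for time observed. An uncollected event therefore lowers the numerator while the participant stays in the denominator. With 120 participants randomised 1:1:1:1, an arm has about 120/4 = 30. One participant whose only TEAE falls in the gap moves that arm's incidence by 1/30, or 3.3 percentage points.

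**Working it through.** The plan gives no figure for the length of this gap, so there is none to reproduce. What follows is day arithmetic under stated assumptions.

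**Inputs**
- Treatment lasts 12 weeks, or 84 days (Brief Summary). Week 12 is Day 85 (Section 10.4.3).
- The study lasts 16 weeks, or 112 days (Brief Summary). Whether this includes screening is not stated.
- Last visit day, L (assumption, because visit days are redacted): L = 112 if the 16 weeks run from Day 1. L = 85 if they include about 4 weeks of screening, so that Week 12 is the last visit counted.
- Stop day, d: illustrative values.

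The sentence in Tables 2-1 and 2-2 is loosely built and might be read as 30 days after participation ends. The reading used here is the one that matches Table 10.4.3-1, and it gives the smaller gap.

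**Formulas**
- Section 9.2.1 window ends on day d + 30.
- Later-of window ends on day max(d + 30, L).
- Gap = max(0, L − (d + 30)). Share of the period = gap / L.

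**Results**

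| Stop day d | 9.2.1 window ends | Gap, L = 112 | Share | Gap, L = 85 | Share |
|---|---|---|---|---|---|
| 1 | 31 | 112 − 31 = 81 | 72% | 85 − 31 = 54 | 64% |
| 15 | 45 | 112 − 45 = 67 | 60% | 85 − 45 = 40 | 47% |
| 29 | 59 | 112 − 59 = 53 | 47% | 85 − 59 = 26 | 31% |
| 57 | 87 | 112 − 87 = 25 | 22% | 0 (87 > 85) | 0% |
| 84 (completer) | 114 | 0 (114 > 112) | 0% | 0 | 0% |

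The gap closes for stops from Day 82 onward if L = 112, and from Day 55 onward if L = 85. Counting the 16 weeks to Day 113 instead of Day 112 adds one day to each non-zero gap in the L = 112 column.

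**What falls in the gap.** Under Section 9.2.1 read alone, these are non-serious AEs and SAEs not judged related. Related SAEs stay reportable. Laboratory tests, ECGs, vital signs and physical examinations follow the schedule, and Section 9.2.1 does not shorten them.

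**The case against.** The best case on the other side is that the rest of the protocol covers the gap. Section 8.1 sends early stoppers to the schedule, whose AE rows hold the later-of rule. The introduction to Section 9 makes adherence to the schedule a requirement. Section 5.1 has AEs recorded at visits and throughout the study period. Section 9.2.3 requires every identified non-serious AE to be recorded, and Section 9.2.8 adds significant worsening found at examinations. Appendix 3 requires SAEs to be reported whether or not related, with no 30-day limit. Section 9.2.1 also sets a minimum and does not forbid later recording.

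Much of this stands. It makes the loss conditional on a site working from Section 9.2.1, and it narrows the likely loss mainly to non-serious AEs. It does not remove the conflict. Section 9.2.1 is the section titled for the collection period, and the AE rows of Tables 2-1 and 2-2 refer back to Section 9.2. Sections 9.2.3 and 9.2.8 say what to record without setting a period. Appendix 3 says how fast to report SAEs and likewise sets no end date.

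The size of the affected group is also open. Section 8.1.1 makes continued follow-up sound optional, and the documents give no expected rate of early stopping. Events in the gap occur more than 30 days off drug, so many may say little about the drug. That is a reason to tabulate them separately. It does not justify leaving their collection to a site's reading.

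**Conclusion.** The inconsistency is real and legible in all four places, and redaction does not explain it. For participants who stop early and remain in the study, Section 9.2.1 closes routine AE and SAE collection before the primary safety time frame closes. The uncovered stretch is 22% to 60% of the period for stops between Day 57 and Day 15 if the last visit is Day 112, and 0% to 47% if it is Day 85. The maximum is about 64% to 72%, for a stop on Day 1. These figures rest on the assumed last visit, on the participant staying to that visit, and on the site following Section 9.2.1.

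A reader might infer three stronger things that the documents do not support:
- *Early stoppers lose about half of their safety follow-up.* No single fraction can be given, because the last visit day is redacted and the loss depends on the stop day. Half is neither the maximum nor typical. Only AE and SAE collection is at issue, and the loss is possible, not certain.
- *The comparison of arms is biased.* That would need early stopping that differs by dose, continued attendance beyond 30 days, and sites that follow Section 9.2.1. It is possible, but neither its direction nor its size can be shown from the documents.
- *A co-primary endpoint fails.* The protocol lists safety among its primary endpoints and summarises it descriptively. It does not call it co-primary, and no hypothesis test depends on it.

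The point is worth correcting because a primary safety endpoint should have one collection window and the correction is small.

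**What to change.** Reconcile Section 9.2.1 with Tables 2-1, 2-2 and 10.4.3-1 by adding the later-of rule they already use: collection runs until 30 days after dosing stops or the last study visit, whichever is later. The same sentence in all four places would also remove the loose wording in the schedule. The definition of treatment-emergent in the SAP should use the same end date. Section 8.1.1 should be brought into line with Sections 8.1 and 8.2 on whether early stoppers are followed.

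If the sponsor wants an on-treatment view, events within 30 days of the last dose can be tabulated separately.

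The cost is one clause in the protocol and a few more AE records for early stoppers, taken at visits already scheduled. No visits or procedures are added.
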